Relatively relaxed enrollment criteria will be employed to include a representative sample of patients with upper extremity motor impairment. Patients who have experienced a stroke (of any etiology) resulting in hemiparesis at least six months prior, have preserved ability to comprehend and participate in basic elements of the therapy, who have corrected vision of at least 20/70 (individuals with low vision would have difficulty participating in the gaming intervention), who are not currently participating in other experimental upper extremity trials, who are not currently engaged in other outpatient rehabilitation for their upper extremity, and who have not received Botox within the last 3 months (confound) will be eligible to participate. Eligible participants will receive an in-person screening to ensure their ability to safely engage in rehabilitation. Patients deemed too frail to undergo intensive rehabilitation or those with serious, uncontrolled medical problems will be excluded (e.g., debilitating pain). The recruited sample will represent approximately 50% of individuals with hemiparesis. Participants will be stratified by severity of impairment (see table below) and separately randomized to reduce potential baseline inequality between groups.

Severity of	Shoulder	Elbow	Wrist	Fingers	Thumb
Impairment					
Mild-	Flexion ≥45° and	Extension ≥20°	Extension ≥20°	Extension of all	Extension or
moderate	Abduction ≥45°	from a 90° flexed	from fully flexed	MCP and (PIP or	abduction of
		starting position	starting position	DIP) joints ≥10°	thumb ≥10°
Moderate	Flexion ≥45° and	Extension ≥20°	Extension ≥10°	Extension MCP	Extension or

Abduction ≥45°	from a 90° flexed	from fully flexed	and (PIP or DIP)	abduction of
	starting position	starting position	joints of at least 2	thumb ≥10°
			fingers ≥10°	

Measurement/Instrumentation

Primary measures:

- Motor Activity Log
- Wolf Motor Function Test

Secondary measures:

- bilateral activity monitors (accelerometers)
- Patient Health Questionnaire (PHQ-9)
- Touch Test Monofilaments
- Neuro-QOL
- 9-Hole Peg Test
- Brief Kinesthesia Test
- Kinematic Analysis (performed on skeletal Kinect data collected during game play)
- Montreal Cognitive Assessment (MoCA)

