Now move your arm back on the armrest so that the palm of your hand is flat o hanging loosely over the front edge of the armrest.	on the armrest and	d your fingers are
Can you lift at least two fingers while keeping your palm in contact with the armrest?	Y	N
Answer the following questions about your weaker arm. It can be placed in any perform these tasks.	v position that ma	kes it easier for you to
Can you straighten your elbow?	Y	N
Can you raise your arm at the shoulder?	Y	N
Can you pick up a tennis ball and release it?	Y	N
Can you pick up a washcloth and release it?	Y	N
PAIN SCREEN		
Do you have pain that interferes with your life or activities?	Y	N
If so, which word or words best describe the pattern of your pain?		
Continuous Periodic (sometimes present) Momen	ntary (lasting a sh	ort time)
What kinds of things relieve your pain?		
What kinds of things increase your pain?		
Please answer each of the following questions using the most appropriate rating and 10=excruciating pain		
Which rating describes it as its worst during the past week?		
Which rating describes it when it is at its least during the past week?		

Which rating describes your pain on average during the past week?

RCT In-Person Participant Screening Form

Date:	Evaluato	or	
Participant's name:			
DOB:			
Gender:			
Race:			
Contact person:			
Address:			
Phone:			
Pre-morbid handedness:			
Side of Hemiparesis:			
Date of Stroke:			
Family and Friends (Required: case we cannot get hold of the		one numbers of family and	friends ir
Name:	Relationship:	Phone:	

ALL BULLETED INCLUSION CRITERIA MUST BE MET

I. Active Movement

1. Active Wrist and Finger Extension:

Starting position: Participant's forearm on supporting surface (in pronation) with hand hanging over edge of supporting surface allowing full wrist flexion or subject's available range of motion.

Participants must be able to actively extend wrist 10° from the starting position, extend or abduct the thumb at least 10° from the starting position and extend the metacarpophlangeal and interphalangeal joints of at least 2 additional digits 10°. Picks up a washcloth from table and releases it. Must be able to perform each activity at least 3 times in 1 minute. Criteria can be met with a device such as Saebo Glove if participant is willing to use this device consistently during the trial.

- Extension of wrist: 10° or more
- Extension or abduction of thumb: 10° or more

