This criterion is most useful for identifying which participants with higher motor functioning are eligible to participate. There is no maximum level of motor ability for the study, but participants must exhibit non-use of the weaker arm (score less than 2.5 on the QOM portion of the MAL). When non-use is obvious and motor impairment is pronounced, you need not administer MAL.

- MAL QOM less than 2.5
- ✓ Does the participant meet these criteria? Y N

VI. Pain

Potential participants will be given the option to self-exclude if they have pain that would be significantly aggravated by participation in the protocol. Consider missed days in carrying out everyday tasks due to pain and excessive discomfort.

VII. Anti-Spasticity Agents:

Participants receiving Botox injections may be scheduled after 12 weeks from when the Botox injection was administered. If the participant is using other antispasticity agents such as oral Baclofen, then that information will be noted but will not used as inclusion / exclusion criteria.

• More than 12 weeks from last Botox injection at start of trial

Are you currently using Baclofen, Dantrium or any other anti-spasticity agen If so, which one?	its? Y	N	
If botox, date of last injection?			
✓ Does the participant meet these criteria? Y N			
VIII. Administer 9-hole peg test			
If participant qualifies, see whether he/she falls in higher or lower functioning growill be based on the participant's ability to complete placement of any number of peg test within the allotted time (120 seconds).			
Higher group: can place ANY number of pegs (1-9) Lower group: cannot place any pegs			
✓ Which group is the participant assigned to?			
IX: Additional Questions			
	(circle one)		
Are you able to maintain standing balance for 2 minutes; using UE for support if needed without the assistance of another person?	Y	N	
Are you able to independently and safely transfer to/from the toilet and manage clothing/hygiene?	Y	N	
Are you able to independently stand from a sitting position?	Y	N	
Do you plan to use a device during the trial (e.g., Saebo)?	Y	N	
X: Summary and Planned Follow-up:			
XI: If enrolled			
Randomization Group?			
Date of Pretest:			
Date of Post-test:			
Date of 6-month follow-up:			

Treatment materials – CI therapy

Checklist

Note: Bolded items are separate sheets within the treatment packet to be completed

Prior to Treatment (after pre-test)

- 1. Provide the activity monitors to participants and demonstrate use.

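### The protocol's severity table and the screening form's peg test give different two-level groupings, and the plan does not say which one is the randomisation stratum

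*Combined protocol and SAP*

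**What the plan says.** The protocol (III. Procedures, Sample & Inclusion/Exclusion Criteria) names one stratification factor and points to a table: "Participants will be stratified by severity of impairment (see table below) and separately randomized to reduce potential baseline inequality between groups". The two rows share the same shoulder, elbow and thumb thresholds and differ in two columns:

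- **Wrist extension:** at least 20 degrees for mild-moderate, at least 10 degrees for moderate.
- **Fingers, 10 degrees in either row:** the mild-moderate row reads "Extension of all" finger joints; the moderate row reads "joints of at least 2" fingers.

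The RCT In-Person Participant Screening Form, section VIII, tells the evaluator, once a participant qualifies, to "see whether he/she falls in higher or lower functioning" group. The test is the 9-hole peg test with 120 seconds allowed: "Higher group: can place ANY number of pegs (1-9) Lower group: cannot place any pegs". The evaluator then answers "Which group is the participant assigned to". The randomisation entry comes later, in section XI.

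Section I of the same form checks movement only at 10 degrees for the wrist and at two additional digits. It also allows a device: "Criteria can be met with a device such as Saebo Glove if participant is willing to use this device consistently during the trial".

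The Data Analysis paragraph gives the primary models treatment, time, their interaction and a random subject effect. There is no stratum or severity term.

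**The concern.** The protocol promises stratification on a joint-range definition of severity. The form that sites complete never records that definition, but does assign a two-level functional group by a different test, between eligibility and the randomisation entry. The two rules measure different things: active range at the wrist and fingers, against success at a fine-dexterity task.

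Three things are at stake:

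- **Balance.** The stated reason for stratifying is to limit baseline inequality. If the list runs on the peg group, that protection covers the table's severity only as far as the two rules agree.
- **Analysis and reporting.** Anyone asked to report or adjust by stratum would have to guess which variable is meant, and could use one on which the trial was not randomised.
- **Reliance on the design.** The primary models carry no severity term, and significant baseline differences are only to be considered in interpretation. Stratification is therefore the main planned protection on this factor.

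**Working it through.** The documents give no sample size, allocation ratio or agreement rate, so there is no figure of the plan's own to reproduce. The first three steps rest on the text; the fourth is an illustration on stated assumptions.

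**Step 1: can the rules disagree?** Take two patients who meet every other entry criterion, including the form's washcloth task and its repetition requirement.

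| Patient | Wrist | Fingers reaching 10 degrees | Pegs in 120 s | Table | Form |
|---|---|---|---|---|---|
| A | 25 degrees | all | 0 | mild-moderate | lower |
| B | 15 degrees | 2 | 1 | moderate | higher |

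Nothing in either rule excludes A or B. How often such patients occur cannot be found from the documents.

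**Step 2: can the table stratum be read off the form?** Classification needs to know whether the wrist reaches 20 degrees and whether all fingers extend. The form's items stop at 10 degrees and two digits. A participant with every movement item ticked could be in either row, so the form does not determine the stratum.

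**Step 3: does any text link the two?** No section maps the peg group to the table, and none says which drives the list. Section VIII does not call its groups strata. The documents give them no other use.

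**Step 4: size if the peg rule is used.** Let *p* be the share of mild-moderate patients by the table, *n* the number per arm, *a* the agreement between the rules and φ their correlation. With both rules splitting the sample equally, φ = 2*a* − 1. Stratifying on the peg group leaves

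SD of the between-arm difference in mild-moderate share = √(2*p*(1 − *p*)/*n*) × √(1 − φ²).

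Assumed: *p* = 0.5 and *n* = 40. Without stratification the SD is √(2 × 0.25/40) = 0.112.

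| Agreement *a* | φ | Imbalance variance removed (φ²) | SD (formula) | SD (simulation) | Chance that two arms differ by more than 15 points (simulation) |
|---|---|---|---|---|---|
| 50% | 0 | 0% | 0.112 | 0.110 | 18% |
| 75% | 0.5 | 25% | 0.097 | 0.097 | 13% |
| 85% | 0.7 | 49% | 0.080 | 0.081 | 6% |
| 95% | 0.9 | 81% | 0.049 | 0.050 | 0.4% |
| 100% | 1 | 100% | 0 | 0.012 | 0% |

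The simulation used four arms, permuted blocks of four within peg group, and 4,000 runs. Its small residual at full agreement comes from incomplete blocks, which the formula ignores. At 85% agreement the SD goes from 0.158 to 0.113 with 20 per arm, and from 0.091 to 0.065 with 60. The proportional reduction, 29%, does not depend on *n*.

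**The case against.** **The form never says stratum.** Only the protocol body names a stratifier. A reader might infer that two rules both define the randomisation stratum, but the peg groups are not described that way and the randomisation entry is a separate item. This stands, and it limits confidence. It does not remove the problem: if the peg group is not the stratum, the form has no field for the stratum the protocol requires.

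**Stratification may work as intended.** A reader might infer that severity is not balanced, or that balance is largely lost. The documents do not support that. If the table drives the list, severity is balanced. If the peg rule does, balance is partial and could be good; at 95% agreement, 81% of the imbalance variance is still removed.

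**No bias follows.** Allocation is random under either rule. The treatment-by-time test also largely absorbs a chance difference in baseline level, so what remains is any difference in change by severity. Suppose the table stratum explained 30% of baseline variance in the Wolf test (assumed). The residual variance factor is then 1 − 0.30 = 0.70 when the rules match and 1 − 0.30 × 0.36 = 0.892 at 80% agreement. The SD ratio is √(0.892/0.70) = 1.13, a modest penalty. This stands too.

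**Sites and devices.** A reader might infer that sites use different rules, or that patients who qualify with a device have no row in the table. Neither is supported. One form is shown and site training is planned, and nothing bars range measured with a device from the table. The protocol simply does not say whether the table's ranges are taken with or without one.

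The document also mentions a separately published protocol, which is not available here and might settle the question. The reviewed text should settle it by itself.

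**Conclusion.** The concern holds as an unreconciled contradiction in the allocation procedure. The protocol table and the screening form give different two-level severity groupings, the same patient can be classed oppositely, no text says which drives the list, and the form cannot yield the table stratum. That the peg group is the stratum is a reasonable inference, not a statement in the documents.

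If the peg rule is the one used, balance on the named factor is partial, to a degree the documents do not allow one to compute. The illustrated range, a 13% to 56% reduction in the SD of chance imbalance at 75% to 95% agreement, rests on equal-sized groups and an assumed agreement rate. The cost is chance balance, precision and clarity of reporting. Should-fix, moderate confidence.

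**What to change.** Name one rule as the stratification factor, and make the protocol's sample section and the screening form agree.

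- **If the peg rule is chosen:** replace the table reference in the stratification sentence. Keep only the moderate row as the entry minimum, since the two-row table cannot serve as one and this row carries the form's wrist, thumb and finger-count thresholds. Reconcile the joint description, because the table accepts PIP or DIP while the form's item names PIP. Also check the 9-Hole Peg Test sheet, whose partly garbled text appears to score an uncompleted test as 0 pegs. A patient who placed some pegs could then be in the higher group yet carry a recorded count of 0.
- **If the table is chosen:** add form fields for wrist extension in degrees and for the number of fingers extending, and remove section VIII as the group assignment.
- **Either way:** state whether the measurement is made with or without a device, and record the stratum as randomised. Add that stratum as a fixed effect to the primary models, preferably with its interaction with time. A main effect alone adjusts level and, with complete data, leaves the treatment-by-time contrast unchanged. For anyone already randomised, state which rule was used.

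The peg option costs wording only. The table option costs two form fields, because those measurements are not on the form now. The model change needs no new data once the stratum is recorded.

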Despite its effectiveness, CI therapy is available to less than 1% of the estimated 1.2 million chronic stroke survivors who could benefit from it. Common barriers to access include dearth of trained providers, cost, insurance caps, and travel/scheduling demands. Although in its infancy, telemedicine is an emerging field with substantial promise to produce exceptional interventions at low cost that can be widely distributed. Most studies to date have found that virtual reality interventions are at least as effective as their low-technology counterparts. To deliver CI therapy to underserved individuals, a novel patient-centered approach to rehabilitation was developed that utilizes newly developed, inexpensive, and commercially available gaming technology (Microsoft Kinect). Initial evidence from a pilot trial of this system suggests that improvements in motor speed, an outcome of prime importance to stroke survivors, are approximately equivalent to those reported in the traditional CI therapy literature. Qualitative data reveal that the technology is accepted irrespective of age, technological expertise, ethnicity, or cultural background. A randomized clinical trial is now required to provide reliable (level 1) evidence of the effectiveness of this novel model of CI therapy delivery.

III. Procedures

Aim 4. To compare the effectiveness of a 3D video game delivery model of CI therapy versus traditional clinic-based CI therapy and standard care in a randomized controlled trial.

Administration

OSU will serve as the lead site for a multi-site trial. Communication between sites will occur through quarterly phone calls (and more frequently if needed) between OSU PI and the PI of the sites. In-person site visits will also occur at the beginning of the project and again after sites have obtained ~25% enrollment. Video-based site visits may replace in-person site visits in some instances as appropriate. Site trainings will occur at each site and will include procedures necessary for maintaining data security and participant privacy (e.g., procedures for uploading study testing forms to secure REDCap database at OSU).

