The central database for the project will be maintained at OSU (REDCap). All records for the study will be scanned in by each site and uploaded to REDCap. Adherence to study treatment and testing protocols will be checked by a blind rater at OSU whose job is to randomly review video-taped treatment and testing sessions. Significant deviations from protocol will be addressed by retraining personnel or termination (if the problems

persist). Video data (e.g., see above) will be transferred to OSU from the other sites via USPS on encrypted storage drives.

Unanticipated problems (from all sites) will be reported to the OSU PI, OSU's central IRB, as well as to the PIs of individual sites. To avoid a potentially large volume of reports of external adverse events, the HHS Office of Human Research Protections (OHRP) has released guidance urging that individual adverse events should only be reported to investigators at all institutions when a determination has been made that the events meet the criteria for an unanticipated problem. OHRP recommends that any distributed reports include: (1) a clear explanation of why the adverse event or series of adverse events has been determined to be an unanticipated problem; and (2) a description of any proposed protocol changes or other corrective actions to be taken by the investigators in response to the unanticipated problem. Adverse event reporting for the proposed research will follow this model.

An initial analysis of data will be conducted at OSU after 50% total recruitment. These interim findings will be shared with other site PIs by the OSU PI. Decisions to modify the protocol based on interim findings will be made jointly between all the sites to ensure protocol consistency. Interim findings that may influence protocol safety and willingness to participate will be reported to the IRBs at each institution by the PIs at each institution.

Research Design

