Measures will be administered within a week prior to beginning treatment, in the week following treatment, and at 6-month follow-up (±1 month). A rehabilitation professional blinded to treatment condition will perform the testing. Reliability of the blinded assessors will be monitored by videotaped assessments reviewed by independent raters.

Additional quality metrics that could create apparent differences in effectiveness in clinical populations will also be measured. After completion of participation, we will survey participants to collect qualitative feedback regarding their experiences with the treatment. Participants will be asked about which therapy condition (traditional CI therapy, gaming CI therapy, standard therapy) they would have preferred under ideal (i.e., cost and transportation are not an issue) and realistic (i.e., their current resources are a consideration) conditions. Differential adherence will also be examined by the proportion of therapy sessions attended, hours of mitt use objectively quantified by a sensor in the mitt, hours of game play, and self-reported compliance with home practice.

Outcome measure	Addresses	Pre	Post	6mo
Motor Activity Log	Nonuse for daily activities	X	X	X
WMFT	Motor speed/function	X	х	X
Grip strength of WMFT ⁹⁹	Weakness	Х	х	X
Kinematics	Weakness, range of motion, motor control, ataxia, poor precision, speed, hypertonicity	х	Х	X
Neuro-QOL	Quality of Life	Х	X	X
Activity monitoring	Nonuse for daily activities	Х	X	X
Brief Kinesthesia Test	Sensory proprioception	Х	х	X
Touch Test Monofilaments	Tactile loss	Х	х	X
Montreal Cognitive Assessment (MoCA)	Cognitive screen	Х		

Survey		X	

Recruitment

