Handling missing data - We will prevent missing data through the use of checklists. These checklists will ensure that all measures are collected at each assessment session in a consistent order according to study protocol. Checklists will also minimize data loss due to technical difficulties (e.g., improper initialization of the bilateral activity monitors, dead batteries, etc.). Automated reminder calls will be sent to participants to reduce missed appointments and to remind participants to wear the activity monitors. Missed appointments will be rescheduled immediately. Testing data will be entered into a secure (and backed-up) REDCap database within 48 hours of data collection. Reasons for drop-out (and whether drop-out was therapist or participant-initiated) will be documented in detail. Loss to follow-up will be minimized by collecting multiple types of contact information and an alternate contact for the participant should he/she be unreachable.

Data Analysis- Missing data from participants who are *unable* to complete the protocol (e.g., due to random factors unrelated to the study protocol) will be removed from analysis via list-wise deletion. An *intent-to-treat analysis* will be carried out such that data from participants who *voluntarily withdraw* from treatment or are unable to tolerate the treatment protocol will be included; the mixed effects model planned for analysis is purely likelihood-based and can make use of all of the data available with no necessary modifications for differing numbers of subjects at each time point. Therapy-induced changes in motor ability (primary outcome measures of accelerometry and WMFT) will be analyzed via *mixed effects linear models*. Initially, separate models will be constructed for the two primary outcome measures. Each of these models will include treatment and time (as well as their interaction) as fixed effects and subject as a random effect. In these models, the *interaction of treatment and time is the primary effect of interest*, since it quantifies the difference in change over time among the four treatment groups. Statistical testing will be used to determine whether individuals lost to follow-up differ from those who completed the study. Demographic measures

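### Site is neither a named stratification factor nor a term in the primary model, and severity is left out of the model too; this costs some precision and is cheap to put right

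*Combined protocol and SAP*

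**What the plan says.** - **Sites.** Under Administration: "OSU will serve as the lead site for a multi-site trial". Sites are trained separately, and recordings are sent in: "Video data (e.g., see above) will be transferred to OSU from the other sites via USPS on encrypted storage drives". That therapists and testers are local is a fair inference, though not stated outright.
- **Randomisation.** Under Sample & Inclusion/Exclusion Criteria: "Participants will be stratified by severity of impairment (see table below) and separately randomized to reduce potential baseline inequality between groups". No other factor is named. Block size, list structure and central or local release are not described.
- **Primary model.** Under Data Analysis: "Each of these models will include treatment and time (as well as their interaction) as fixed effects and subject as a random effect". The effect of interest is the treatment-by-time interaction. Site and therapist are not among the potential moderators in Aim 4b either.
- **Control of staff variation.** Treatment and testing videos are checked by a blind rater at the lead site. Under Measurement/Instrumentation: "A rehabilitation professional blinded to treatment condition will perform the testing", and "Reliability of the blinded assessors will be monitored by videotaped assessments reviewed by independent raters".

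**The concern.** The random subject effect absorbs stable differences in level between sites. The primary effect, however, is a difference in change, and sites can differ in change through therapist skill, tester drift or case mix. With four arms and perhaps 8 participants per arm at each site, severity-only randomisation can leave the arms uneven within a site. Site variation in change then adds noise to every arm contrast. The same reasoning applies to severity: it is the one factor chosen for stratification, yet it is absent from the analysis. What is at stake is efficiency, not the validity of the comparison.

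**Working it through.** **Inputs.** From the documents: four arms, two severity strata, three assessment times, and the model terms above. Not given, so assumed: N of 120 to 200, 4 or 5 sites, equal allocation, permuted blocks of 8 within severity, two-sided 5% tests, and site explaining a share ρ = 0.02 to 0.10 of the variance in change. The plan states no figure to reproduce. The calculations use a single change score, which simplifies the three-visit model.

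**1. Imbalance within sites.** At N = 160 and 5 sites the expected count is 160/5/4 = 8 per arm per site. In simulation the mean gap between the largest and smallest arm at a site is 5.2 participants with severity-only strata, and 1.7 when site is also a stratum. Over N = 120 to 200 the gap falls from 4.9–5.8 to 1.5–1.7.

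**2. Bias and type I error when site is ignored.** Two-arm comparison of change at N = 160 and 5 sites, with no site stratification (8,000 runs, Monte Carlo standard error about 0.0024):

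| Site share of variance | Type I error, site not a stratum | Type I error, site a stratum but not in the model |
|---|---|---|
| 0.02 | 0.048 | 0.049 |
| 0.05 | 0.048 | 0.045 |
| 0.10 | 0.054 | 0.041 |

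The mean estimated difference was about zero throughout. Ignoring site therefore neither biases nor inflates. Stratifying on a factor and then leaving it out makes the test conservative. The same would apply to severity to the extent that it predicts change; the documents allow no figure for that.

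**3. Precision.** Take the variance of a pairwise contrast in the planned model as 1. With site in the model it becomes (1 − ρ)/e, where e is the efficiency kept after estimating site effects.

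- With site as a stratum, e is about 0.995 (simulated at N = 160, 5 sites).
- Without site stratification, in the four-arm model, e is about 1 − (S − 1)/(N − 4) for S sites. For 120/4 this is 1 − 3/116 = 0.974; for 160/4, 1 − 3/156 = 0.981; for 160/5, 1 − 4/156 = 0.974; for 200/5, 1 − 4/196 = 0.980.

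The reduction in variance is 1 − (1 − ρ)/e:

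| ρ | Stratify and model (e = 0.995) | Model only (e = 0.974 to 0.981) |
|---|---|---|
| 0.02 | 1 − 0.98/0.995 = 1.5% | −0.6% to 0.1% |
| 0.05 | 1 − 0.95/0.995 = 4.5% | 2.5% to 3.2% |
| 0.10 | 1 − 0.90/0.995 = 9.5% | 7.6% to 8.3% |

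In round figures, the gain is 2% to 10% with both changes, and none to 8% with the model terms alone. Simulating the allocations and taking the exact variance from the design matrix gives the same ranges.

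**4. Therapist, as a conditional case.** If each therapist treated one arm only, with m participants each and within-therapist correlation ICC, the design effect is 1 + (m − 1)ICC and the actual error is 2[1 − Φ(1.96/√design effect)].

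- m = 5, ICC 0.02: 1 + 4(0.02) = 1.08, error 5.9%.
- m = 10, ICC 0.05: 1 + 9(0.05) = 1.45, error 10.4%.
- If only one of the two compared arms is clustered, the design effects average to (1 + 1.08)/2 = 1.04 and (1 + 1.45)/2 = 1.225, giving errors of 5.5% and 7.7%.

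**The case against.** **The documents do not rule out per-site lists.** They reproduce only the trial sections of an ethics application and refer to a published protocol. This stands: one can say that site stratification is not stated, not that it was absent. The model point survives, because stratifying by site and leaving it out makes the test conservative.

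**Imbalance can be made to look alarming.** Under simple randomisation, the chance that at least one site has twice as many in one arm as in another is 93% to 99%. A reader might infer that the contrasts are compromised. But that figure takes the worst pair of arms at the worst site. For one prespecified pair at one site it is 16% to 24%, and the resulting random error is already reflected in the standard error.

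**Therapist clustering.** A reader might infer that tests at a nominal 5% really run at 6% to 10%. That requires therapists tied to a single arm, which the documents do not say. If therapists treat in all arms, an additive therapist effect largely cancels. Contact time is also high only in Group 1 (35 hours); Groups 2 and 4 have 5 hours each.

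**Conduct safeguards.** Site training, central video review and blinded assessors should reduce site and tester variation. This is fair, and argues for the lower end of the range of ρ. It does not account in the analysis for what remains.

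**Conclusion.** The point holds as a cheap improvement. Severity is the only stratum named, and neither site nor severity is in the stated primary model. The cost is precision: about 2% to 10% of the variance of a contrast if site explains 2% to 10% of the variance in change, with N of 120 to 200 at 4 or 5 sites. All of these inputs are assumed, since the documents give none of them. The documents do not support a claim of bias or of inflated type I error from omitting site. Any therapist effect on type I error remains conditional on a therapist-to-arm structure that is not described.

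**What to change.** 1. State the randomisation method, and generate the allocation in permuted blocks within site and severity.
2. Add site, severity, site by time and severity by time as fixed effects to each primary model. Site is already recorded on the Wolf Motor Function Test form. Settle this wording before the analysis planned at 50% recruitment.
3. Say which severity definition is used. The Sample section defines the strata by active range of motion, while item VIII of the in-person screening form groups participants by 9-hole peg placement. The two must be reconciled before severity can be a stratum or a model term.
4. If enrolment is under way without site stratification, add the model terms alone and accept the smaller gain.
5. State whether therapists treat in one arm or several, and record the treating therapist in all four arms. As a sensitivity analysis only, fit a therapist-by-time random effect; a therapist intercept alone would model level, not change.

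**Cost.** A setting on the randomisation list, some analysis wording, and a few degrees of freedom: for one change score with 5 sites and 2 severity levels, 4 + 1 = 5. The Usual Care Treatment Log, which shows no therapist field, needs one added.
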